In our subsequent YELLOW II study, all patients with obstructive NTL received high-dose statin therapy for 8-12 weeks (22). The aim of the study was to characterize the relationship between the changes in plaque morphology assessed by NIRS/IVUS and OCT, HDL functionality and gene expression in peripheral blood mononuclear cells (PBMC) using microarray analysis. At the follow-up, we observed a significant increase in fibrous cap thickness (FCT) in the study lesion, enhancement of cholesterol efflux capacity (CEC) and significant perturbations of PBMC transcriptome in patients with stable coronary artery disease (CAD) treated with 40 mg rosuvastatin for 8-12 weeks. As a result, the prevalence of TCFA reduced from 20 to 7% (P=0.003) and there was a significant independent association between the thickening of the fibrous cap and improved CEC independent of lipid lowering and CRP reduction. In addition, we observed significant transcriptomic perturbations in genes related to cholesterol synthesis, regulation of fatty acid unsaturation, cellular cholesterol uptake, efflux and inflammation suggesting that several independent molecular mechanisms might be responsible for the beneficial effects of statin on plaque morphology. The unique translational combination of multi-modality intravascular imaging with clinically relevant cellular biology and comprehensive transcriptomics represents a powerful approach to assessing the effects and mechanisms of the efficacy of different lipid-lowering therapies for stabilizing atherosclerotic plaques.

With OCT imaging, we observed an increase in FCT after intensive statin therapy only in a subset of the study patients. Traditionally, response to statins is measured by the changes in serum lipids, however, these changes do not predict the beneficial changes in FCT, therefore, it is important to distinguish statin responders from non-responders using non-invasive methods. In our recent analysis, YELLOW II transcriptomic data was used to predict whether a patient's FCT increased in response to statin therapy using machine learning models (23). One of the model used 18 genes and was able identify statin responders with an accuracy of 95.7%, sensitivity of 94.3% and specificity of 97.1%.

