Hypothesis. In the YELLOW III study, we hypothesize that LDL-C lowering with evolocumab 140 mg every 2 weeks will result in a significant increase in OCT-defined minimal FCT and reduction of plaque lipid content assessed by NIRS compared to baseline in patients with CAD undergoing percutaneous coronary intervention (PCI). In addition, we hypothesize that there is an association between the changes in patient's plaque characteristics and PBMC gene expression and lipid metabolites at the baseline, which would allow us to develop a predictive model for detecting subjects that demonstrate the greatest response regarding plaque morphology to PCSK9 inhibition therapy. YELLOW III will provide an additional contribution to the ongoing HYUGENS study due to its unique design combining intravascular imaging and transcriptomic based machine learning approach, which will allow to uncover molecular mechanisms responsible for the beneficial changes in atherosclerotic lesions of patients treated with evolocumab.

STUDY OBJECTIVES

The aim of the study is to assess the effect of evolocumab on coronary plaque morphology using intravascular imaging, NIRS/IVUS and OCT, and PBMC gene expression analysis in patients with stable CAD on maximally tolerated statin therapy.

Primary endpoints. The primary end-points are the changes from baseline to follow-up (follow-up value minus baseline value) in (1) the minimal FCT assessed by OCT and (2) NIRS maxLCBI4mm after 26 weeks of evolocumab.

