Secondary endpoints. The secondary endpoints are the changes in (1) the maximal lipid arc, lipid length, lipid volume index, macrophage accumulation and calcification by OCT; (2) PAV and TAV defined by IVUS and (3) PBMC gene expression. In recognition of the role of lipids in CAD and atherosclerosis, we will perform lipidomics to analyze lipid metabolites and lipid derivatives in blood plasma and serum in order to identify CAD biomarkers. Measuring lipid metabolites (and their effectors) might directly lead to the identification pathways of lipid action or lipid metabolism in patients receiving treatment. We will also perform Mass Cytometry (CyTOF) of PBMC to characterize the immune profile and responses in patients receiving a combination of evolocumab plus statin with an eye on identifying biomarkers for detecting and/or predicting favorable changes in plaque morphology as a result of PCSK9 inhibition therapy. Other parameters including the levels of CRP, resistin, adiponectin, perilipin and Lp(a) will also be measured for the same purpose.

Exploratory endpoints. Major Adverse Cardiac Events (MACE) will be defined as a combined clinical endpoint of death, MI (Q wave or non Q-wave with CK-MB >3 times above the upper normal limit (48 U/L), urgent revascularization or stroke at 30 days and 1 year.

STUDY PROCEDURES

This is a single center single arm study, which will be performed in the Cardiac Catheterization laboratory of the Mount Sinai Hospital, New York, NY. After informed consent, patients undergoing clinically indicated elective PCI with a non-obstructive lesion and optimal background statin therapy will be eligible for screening (Figure 1). Non-obstructive lesions (30-50% stenosis) identified by angiography in a non-culprit vessel with lipid-rich plaque will be studied. Subjects will receive evolocumab 140 mg subcutaneously every 2 weeks for 26 weeks. Serial NIRS/IVUS and OCT imaging will be performed in the non- obstructive lesions, first during PCI and subsequently after 26 weeks.

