 Screening. Written informed consent must be obtained from all subjects before any study-specific procedures are performed. We will screen patients scheduled for elective coronary angiography and/or coronary artery stenting, who are receiving statin therapy for at least 4 weeks or with history of statin intolerance (should not exceed 20% of the total cohort) with acceptable LDL-C levels. Patients with nonobstructive lesion (30-50% stenosis) by angiography and lipid-rich plaque with lipid arc >90° and minimal fibrous cap thickness ≤ 120 µm detected by OCT will comprise the final study population. Women of childbearing potential will undergo urine pregnancy testing. If necessary, we may request serum pregnancy testing to confirm equivocal urine-based results.

- 2. PCI and baseline imaging. Culprit vessel PCI will be performed according to best current practice. During the same angiographic procedure baseline OCT and NIRS/IVUS imaging of the non-obstructive study lesion will be performed after administration of intra-coronary NTG. A total of 25ml of blood will be drawn from the sheath during angiography for transcriptomic profiling of PBMC (mRNA and miRNA), lipidomics and cytokine analyses. Patients will undergo assessment of lipid levels, CK-MB, Troponin I, liver function, CBC, and hsCRP.
- 3. **Study drug allocation.** All patients will receive subcutaneously administered evolocumab 140 mg every 2 weeks for 26 weeks in addition to statins. Evolocumab will be administered on day 1 (the day of the first treatment) and through week 26 with a personal injector or prefilled auto injector/pens.
- Clinical visits. Study visits will occur during screening (day 1), weeks 12 and 26 (time of follow-up procedure). Subjects must fast overnight when fasting lipid samples are to be obtained.
- 5. Follow up Procedure. The follow-up procedure will be scheduled 26 weeks after the baseline PCI and should occur within ±2 weeks of their specified date. First, routine angiography to check the previous stent will be performed, then, repeat NIRS/IVUS and OCT of the non-obstructive study lesion will be performed after administration of intra-coronary nitroglycerin. A total of 25ml of blood will be drawn

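### Entry is cut at minimal FCT ≤120 µm, apparently at the session that supplies the baseline, so regression to the mean can raise the single-arm FCT change by an amount the documents cannot fix

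*Combined protocol and SAP*

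**What the plan says.** All references are to the combined protocol and SAP.

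- **Endpoint** (Study Objectives, Primary endpoints): "The primary end-points are the changes from baseline to follow-up (follow-up value minus baseline value) in (1) the minimal FCT assessed by OCT", after 26 weeks of evolocumab. The Hypothesis paragraph predicts an increase in minimal FCT. The stated aim is causal: "The aim of the study is to assess the effect of evolocumab on coronary plaque morphology using intravascular imaging".
- **Design** (Study Procedures, opening paragraph): "This is a single center single arm study". Serial imaging is done "first during PCI and subsequently after 26 weeks".
- **Entry** (item 1, Screening): lesions with a lipid arc above 90° and "minimal fibrous cap thickness ≤ 120 µm detected by OCT will comprise the final study population". The Inclusion criteria repeat the 120 µm limit.
- **Baseline imaging** (item 2): "During the same angiographic procedure baseline OCT and NIRS/IVUS imaging of the non-obstructive study lesion will be performed". Item 4 places the screening visit on day 1. No separate screening OCT is described.
- **Reading and analysis** (item 7): images go to an off-line core laboratory blinded to presentation and treatment. The item does not say whether eligibility uses that reading or an on-site one, or which of them is the baseline value. It labels each patient a responder or non-responder by the sign of the FCT change.
- **Background statin** (item 1): patients "who are receiving statin therapy for at least 4 weeks or with history of statin intolerance".

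The text available for this review gives no FCT mean, SD, repeatability, screen-failure rate, sample size or primary test, and no analysis of selection on FCT. The opening of the document and Figure 1 were not available, so absence is claimed only for the text that was.

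**The concern.** A one-sided cut on a variable measured with error over-represents lesions that read thin by chance. If the same error enters the baseline value, the repeat reading is expected to be thicker even when nothing has changed. A concurrent control arm would show the same artefact and cancel it; a single arm cannot.

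The artefact runs in the direction of the hypothesis. It could inflate the estimated change in the first primary endpoint and raise the chance of a nominally significant increase with no drug effect. It also affects the responder label, so the predictive model would be trained partly on noise in the baseline reading.

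**Working it through.** **Inputs from the documents.** The cut is 120 µm, there is one arm, and the endpoint is follow-up minus baseline. The plan states no figure that could be reproduced.

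**Assumed inputs.**
- Screened minimal FCT is normal with mean μ = 80, 100, 120 or 140 µm and between-lesion SD sb = 30, 40 or 50 µm.
- Measurement SD is sw = 5, 10, 15 or 20 µm. With the values above, this makes 48 cells.
- A fraction s of the error variance is common to the qualifying and baseline readings.
- n = 110, the last interim DSMB milestone in item 8 and not a stated sample size.
- The test is a two-sided 5% paired test, and there is no drug effect.
- A second run adds a 20 µm SD of real change between sessions.

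**Formula.** With st = √(sb² + sw²) and z = (120 − μ)/st:

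shift = s × (sw²/st) × φ(z)/Φ(z); share failing the cut = 1 − Φ(z).

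**One cell in full (μ 120, sb 40, sw 15).**
- st = √(1600 + 225) = 42.7, z = 0, and φ/Φ = 0.399/0.5 = 0.798.
- With s = 1, shift = (225/42.7) × 0.798 = 4.20 µm.
- The simulated SD of change is 20.8 µm, so the noncentrality is 4.20 × √110/20.8 = 2.12 and rejection is 56%. With the extra 20 µm SD, the SD of change is 28.8 µm and rejection is 33%.
- With s = 0.5, the shift is 2.10 µm and rejection 18% (12% with the extra SD). With s = 0.25, it is 1.05 µm and 8% (7%).

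**Whole grid.** Rejection comes from the noncentral t.

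| Error variance shared | Shift, µm | Rejection | Rejection, extra 20 µm SD | Cells above 50% (of 48; extra SD) |
|---|---|---|---|---|
| 0 | 0 | 5% | 5% | 0; 0 |
| 25% | 0.04 to 3.3 | 5 to 23% | 5 to 17% | 0; 0 |
| 50% | 0.08 to 6.6 | 5 to 68% | 5 to 51% | 2; 1 |
| 100% | 0.15 to 13.1 | 5.6 to 99.9% | 5.1 to 98% | 14; 7 |

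Rejection is at or below 10% in 39 of 48 cells at 25% shared (44 with the extra SD) and in 25 at 50% shared (34).

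**What drives the size.** With fully shared error, by screened mean:
- 80 µm (9 to 23% of lesions fail the cut): 0.15 to 2.9 µm.
- 100 µm (26 to 36% fail): 0.28 to 5.3 µm.
- 120 µm (50% fail): 0.40 to 8.9 µm.
- 140 µm (64 to 74% fail): 0.53 to 13.1 µm.

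The large values mostly need half or more of the screened lesions to fail. With 50% shared and a mean of 80 or 100 µm, rejection never exceeds 17% (13% with the extra SD).

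**Responder label.** With no effect and no shared error, 50% would be labelled as increased. The share rises to at most about 54% with 25% shared, and to 51 to 69% with 100% shared (50 to 65% with the extra SD).

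**Cross-check.** A separate parameterisation (mean 80 to 120 µm, total SD 30 to 40 µm, reliability 0.70 to 0.95) gave 0.3 to 9.6 µm fully shared, 0.1 to 4.7 µm half shared, and about 0 with independent error.

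**The case against.** The strongest reply is that item 7 already sends images to a blinded core laboratory, so the baseline may be a second reading, distinct from the one that admitted the patient. In that case the fully shared row overstates the problem. This stands in part. A second reading of the same pullback removes reader error, but acquisition error and short-term variation in the lesion stay shared. Blinding to presentation and treatment does not address selection.

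It is also fair that every size input is assumed, that no passage says outright that eligibility and baseline share a session, and that Figure 1 might show the order of imaging. These points limit the claim to a possible bias of known direction and unknown size. They do not remove the mechanism.

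A third objection is that a correction is weakly informative, because a log of screened readings identifies neither s nor the repeatability SD. For readings like those in the 120/40/15 cell, s from 0 to 1 and a repeatability SD of 5 to 20 µm give corrections from 0 to (400/42.7) × 0.798 = 7.5 µm. That is right, and it is why the correction should be shown as a range and not as a corrected estimate.

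A reader might infer that the test would certainly exceed its nominal level, or that an observed FCT increase would be an artefact. The documents support neither: the rate stays at 5% if no error is shared and is close to 5% in many cells. Nor does the point extend to maxLCBI4mm, which has no entry cut-off.

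**Conclusion.** The concern holds as a possible upward bias in the FCT change and in the responder label. The direction is clear wherever the qualifying and baseline readings share error. The size is not known: it runs from nothing to 6.6 µm at up to half of the error variance shared, and to 13.1 µm if the qualifying reading is itself the baseline. It is small if few lesions fail the cut, repeatability is high or little error is shared. The conclusion rests on the inference that both readings come from the PCI session, and on the assumed FCT distribution, measurement error, test and n = 110. It should be fixed; confidence is medium.

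A separate limit applies even if this bias is nil. For 8 to 12 weeks of statin in the earlier YELLOW II study, the plan reports that "we observed a significant increase in fibrous cap thickness (FCT) in the study lesion", while this trial requires only 4 weeks of prior statin. Without a control, an FCT gain larger than regression to the mean still could not be assigned to evolocumab.

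**What to change.** Add to item 7, Data analysis:

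1. Baseline minimal FCT is the blinded off-line core-laboratory reading, separate from the eligibility reading, and no enrolled patient is dropped on it. This removes reader error only.
2. The numeric qualifying FCT of every OCT-screened lesion, including those above 120 µm, is recorded when eligibility is decided, and the screen-failure rate is reported. A number read later for a failed lesion is not its qualifying reading.
3. The raw mean change stays the primary result. Beside it, a pre-specified sensitivity analysis subtracts s × se² × f(120)/F(120). F(120) is the share of logged readings at or below 120 µm, f(120) is their density there, and se is the repeatability SD. It is shown for s from 0 to 1 and a range of se fixed in advance (for example 5 to 20 µm), as a range, because the log identifies neither s nor se.
4. The responder share is reported beside the share expected with no effect over the same range.
5. The FCT result is described as change from baseline, not as an effect of evolocumab. This also covers the missing control for background statin or time.

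The density form in (3) needs normal measurement error with constant SD, but not normal FCT. With log-normal FCT it gave 0.98 to 1.04 times the true shift, against 0.90 to 1.69 for the normal formula. Readings that bunch at 120 µm would weaken it.

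**Cost.** No extra patients or procedures. Numeric readings are needed for failed lesions: about 11 per 110 enrolled if 9.4% fail (110 × 0.094/0.906) and about 320 if 74.5% fail (110 × 0.745/0.255). The sensitivity analysis will show a less favourable FCT figure, and its range depends on assumed s and se. Sampling error in the log adds an SD of about 0.1 to 1.3 µm, a figure that treats s and se as known and so understates the uncertainty.

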from the sheath during angiography for transcriptomic profiling of PBMC (mRNA and miRNA), lipidomics and cytokine analyses.. All study patients will undergo repeat assessment of lipid levels, CK-MB, Troponin I, liver function, CBC, and hsCRP. Bivalirudin or Heparin will be used as anticoagulation as per standard PCI protocol. All patients will have repeat CK-MB and TnI levels measured at 6-8 hours and if in hospital, 16-24 hours post PCI, and thereafter if levels continue to rise

- 6. Post Follow-up. After the follow up procedure patients will be referred back to their primary care physician as is our usual practice. All further adjustment of lipid lowering and other medications will be at the discretion of the primary care physician. The treatment received after 26 weeks of evolocumab will be documented, and clinical telephone follow up will be performed at 30 days, 6 months and 1 year after the follow-up procedure
- 7. Data analysis. Off-line image analysis will be performed by the Mount Sinai Intravascular Imaging core laboratory, which will have no knowledge of patient clinical presentation and treatment.. Statistical and bioinformatics analyses will be performed by an independent biostatistician unaware of clinical data.

For predictive model construction, each patient will be identified as an evolocumab responder or non-responder depending on whether FCT increased or decreased after the treatment. Similar to our YELLOW II transcriptomic sub study (23), an elastic net regularized generalized linear model and K top scoring pair (KTSP) classifier model will be built using clinical variables and PBMC transcriptomic, lipidomics and cytokine analyses data to predict changes in FCT to ascertain whether a patient's FCT will increase in response to treatment. The transcriptomic data will be pre-processed to identify the

mechanism of missing data, and data imputations will be performed for non-ignorable missing data. The accuracy, sensitivity and specificity of both algorithms will be evaluated in order to select the highest performing model. We believe that the predictive model might allow patients to have their FCT response approximated without undergoing intravascular imaging.

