8. Safety reporting. Subjects will be carefully monitored during the study for possible Adverse Events (AEs) from the time of enrollment to the completion of their participation in the study. All adverse events will be fully investigated by the Principal Investigator, classified according to the current definitions of the International Organization for Standardization (ISO) and reported to the Mount Sinai Hospital IRB and Amgen Safety. Timeframes for submission of safety data and aggregate reports to Amgen are described in Tables 1 and 2.

In addition, an independent data and safety monitoring board (DSMB), comprising 3 cardiologists with extensive clinical research experience will oversee this study. The DSMB will be informed within 24 hours of all major adverse events (MACE) defined as a combined clinical endpoint of death, MI (Q wave or non Q-wave with CK-MB >3 times above the upper normal limit (48 U/L), urgent revascularization or stroke at 30 days and 1 year. All minor adverse events will be reported to the DSMB within 5 working days of knowledge of the event. The DSMB will convene after 30, 70 and 110 patients have completed the final procedure and at study closure. The DSMB will have complete discretion to adjudicate all events (major and minor), and, after fair deliberation and at any stage of the trial, to recommend the termination of the study, for whatever reason as they see fit insofar as it may pertain to adverse event occurrence(s). If the DSMB is to recommend termination of the study, the investigators will be given a single opportunity to respond to any concerns the DSMB may raise. After final consideration, if the DSMB again recommends termination of the study, then the study will be terminated. The DSMB may only terminate the study on the basis of MACE and adverse events.

9. Institutional Review Board (IRB). Prior to study initiation and when amended, the study protocol and will be submitted for review and approval to the Icahn School of Medicine at Mount Sinai IRB. Site personnel must provide reports of the progress, or completion, termination or discontinuation of the study to the institutional IRB at appropriate intervals. The primary investigator will verify that each subject has consented, in writing, to direct access to his/her original medical records for trial-related monitoring, audit, IRB/IEC review, and regulatory inspection

Inclusion criteria:

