- Men or women aged 18 years or older at screening who signed written Informed Consent
- Patients with coronary artery disease undergoing cardiac catheterization and PCI for a culprit lesion, who also have a non-obstructive study lesion (30-50% stenosis) identified by angiography in a non-culprit vessel.
- Patients with non-obstructive coronary artery disease and a 30-50% lesion identified by angiography
- Patients who are not candidates for PCI or CABG over the next 12 months, in the opinion of the investigator
- Patients treated with statins for at least 4 weeks with LDL-C level ≥ 80 mg/dL for low- or moderate -intensity statin use and ≥ 60 mg/dL for high-dose statin at screening (Table 3). Patients with history of statin intolerance and LDL-C ≥ 100 mg/dL.

- Angiographic criteria: 30-50% reduction of lumen diameter in addition to the target study lesion. The study segment should not have a history of percutaneous coronary intervention (PCI) or coronary artery bypass grafting (CABG), and may not be a bypass graft.
- OCT criteria: study lesion should have a lipid-rich plaque with lipid arc >90° and fibrous cap thickness ≤120 µm.
- Women of childbearing potential must agree to be on an acceptable method of birth control/contraceptive

Exclusion criteria:

- Patients who have acute myocardial infarction (Q wave or non-Q wave with CK-MB > 5 times above the upper normal (31.5 ng/ml) within 72 hours)
- Patients who are in cardiogenic shock
- Patients with left main disease or patients requiring coronary artery bypass graft surgery
- Patients with elevated CK-MB (>6.3 ng/ml) or Tnl (>0.5 ng/ml)
- Patients with platelet count < 100,000 cell/mm³
- Patients who have co-morbidity which reduces life expectancy to one year
- Patients who are currently participating in another investigational drug/device study
- Patients with liver disease
- Patient with creatinine > 2.0 mg/dL
- Pregnant women and women of childbearing potential who intend to have children during the duration of the trial
- Patients having undergone heart transplantation, or those that may undergo heart transplantation during the study period
- Patients with active autoimmune disease

Table 1. Timeframes for submission of safety data and aggregate reports to

Amgen

Safety Data	Timeframe for submission to	Send to
	Amgen	
Suspected Unexpected Serious	At time of regulatory submission	Amgen Safety
Adverse Reaction (SUSARs)		
Pregnancy/Lactation exposure	Within 1 business day of Sponsor	Amgen Safety

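### As defined, a survived spontaneous non-Q-wave MI with no qualifying CK-MB value and no urgent revascularization is left out of MACE and of the 24-hour DSMB notice

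*Combined protocol and SAP*

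**What the plan says.** **Definition.** Under Study Objectives, Exploratory endpoints, MACE at 30 days and 1 year combines death with "MI (Q wave or non Q-wave with CK-MB >3 times above the upper normal limit (48 U/L), urgent revascularization or stroke". Troponin is not mentioned.

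**DSMB clock.** Study Procedures, item 8 (Safety reporting), repeats the definition and ties the fast route to it: "The DSMB will be informed within 24 hours of all major adverse events (MACE) defined as a combined clinical endpoint of death, MI". The only other route is: "All minor adverse events will be reported to the DSMB within 5 working days of knowledge of the event". Item 8 also lets the DSMB adjudicate events of either grade and recommend termination at any stage because of adverse events.

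**Marker schedule.** Both markers are drawn at baseline (item 2: "Patients will undergo assessment of lipid levels, CK-MB, Troponin I, liver function, CBC, and hsCRP") and at week 26 (item 5: "All study patients will undergo repeat assessment of lipid levels, CK-MB, Troponin I, liver function, CBC, and hsCRP"). Item 5 adds CK-MB and troponin I at 6-8 hours after PCI, and at 16-24 hours if the patient is still in hospital. The one visit in between, at week 12 (item 4), has no cardiac marker named. After the second procedure, item 6 states that "clinical telephone follow up will be performed at 30 days, 6 months and 1 year after the follow-up procedure".

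**Entry.** The exclusion criteria use either marker as a screen: "Patients with elevated CK-MB (>6.3 ng/ml) or Tnl (>0.5 ng/ml"). A separate exclusion defines acute MI by Q wave or by CK-MB above 5 times the upper normal value.

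**The concern.** The definition asks for a laboratory value that the plan obtains only around two planned procedures. Spontaneous MIs can occur at any time in the 26 weeks on evolocumab and in the following year. For those, the trial depends on whatever the treating hospital recorded. If that record holds troponin but no CK-MB, a non-Q-wave MI cannot satisfy the definition, however clear the clinical picture.

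Two things are at stake. First, the reported MACE rate: the study has a single arm, so no control group shares the omission, and the rate is simply lower than the true one. Second, timing: because the MACE definition also triggers the 24-hour notice, an MI that fails it moves to the slower route.

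**Working it through.** The plan states no figure for this point, so the check is to set the definition, the marker schedule and the reporting rule side by side.

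**Step 1. Can any reading of the CK-MB cut-off admit troponin?**
- If 48 U/L is the threshold, the implied upper limit is 48 / 3 = 16 U/L.
- If 48 U/L is the upper limit, the threshold is 3 × 48 = 144 U/L.
- The acute MI exclusion gives 31.5 / 5 = 6.3 ng/ml, which matches the CK-MB entry limit. Three times that limit is 18.9 ng/ml, in a different unit from the MACE cut-off.

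No reading brings in troponin. The ambiguity of the 48 U/L figure is a separate matter.

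**Step 2. Classify each kind of MI under the text as written.**

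| Event | MACE? | DSMB notice |
|---|---|---|
| Q-wave MI, any marker | Yes | 24 hours |
| Non-Q-wave MI, CK-MB above cut-off | Yes | 24 hours |
| Non-Q-wave MI, no qualifying CK-MB, followed by death | Yes, as death | 24 hours |
| Same, with urgent revascularization | Yes, as revascularization | 24 hours |
| Same, survived, no urgent revascularization | **No** | **5 working days** |

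Only the last row is affected. The text names no third route, so an MI that is not MACE falls to the one for minor events.

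**Step 3. When could the last row arise?** Around the procedures CK-MB is drawn alongside troponin, so a periprocedural MI above the cut-off is caught. Outside those windows, from the baseline procedure to week 26 and for one year afterwards, the plan draws neither marker to a schedule. Classification then rests on outside records, and the text has no step to obtain CK-MB and no rule for a record without it.

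**Step 4. How many events?** This cannot be computed. The text gives neither an MI rate nor the share of MIs documented by troponin only.

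**The case against.** The strongest reply is that the gap is narrow and the oversight is intact. Most of this stands.

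- A reader might infer that every MI documented by troponin alone is lost. That is too broad: Q-wave MIs, deaths and urgent revascularizations count whatever the marker.
- A reader might infer that the DSMB works from an incomplete set of events. Item 8 does not support that: all adverse events are reported, the DSMB may adjudicate any of them, and no stopping rule is tied to an MI count. The cost is delay. For an event first learned of at a telephone call, possibly about 6 months after the previous one, a few further working days add little.
- A reader might see a contradiction in using troponin at entry but not for MACE. The acute MI exclusion is also defined by CK-MB, so the protocol's concept of MI is consistent. The troponin line is a separate screen for a raised marker.
- A reader might size the loss from the 110 patients in item 8. Assuming a 2-4% MI rate and a 25-50% troponin-only share gives 110 × 0.02 × 0.25 = 0.55 to 110 × 0.04 × 0.50 = 2.2 events. Neither percentage has a source in the documents, 110 is a DSMB meeting milestone and not a stated sample size, and the product is not reduced for events that already count. It should not be used.
- Nothing in the documents says that outside hospitals measure troponin without CK-MB.

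What the reply does not remove is the last row of the table. DSMB discretion operates after notification, and the text gives it no troponin criterion to apply.

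**Conclusion.** The point holds in narrow form. As written, a spontaneous non-Q-wave MI that is survived, without urgent revascularization and without CK-MB above the cut-off, is not MACE. It reaches the DSMB within 5 working days of knowledge instead of 24 hours.

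The number of such events is unknown and may be zero. The conclusion about the rule needs no assumed rate; whether it changes the count depends on at least one such MI occurring. MACE is exploratory in a single-arm study, so no hypothesis test or primary endpoint is affected. This is a worthwhile low-cost improvement to the safety count and its timing, not a threat to the trial's main conclusions.

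**What to change.** Make the same change under Exploratory endpoints and in item 8 (Safety reporting):

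1. Add that an MI not related to a PCI also qualifies as MACE when documented by troponin with clinical evidence of ischaemia. The sponsor sets the exact criterion.
2. Keep the CK-MB criterion for procedure-related MI, and say whether an MI after the week-26 imaging procedure without PCI belongs to that group.
3. Record the qualifying marker on the case report form.
4. Report the two MI types separately.

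The cost is definition text and one form field. The downsides are a slightly higher MACE rate and less direct comparison with studies that use CK-MB only; separate reporting offsets the second, because the CK-MB-based count can still be read off.
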